b. Interventions. After recovery from surgery, *post-implant, pre-intervention* behavioral and cardiovascular assessments will be conducted (Appendix #1). Mapping of the motor evoked responses related to spatial electrode selection, amplitude and/or frequency [72] will be conducted and the specific configurations and parameters optimal for voluntary movement, standing and cardiovascular function will be identified. The pattern of electrically active electrodes, as well as electrode amplitude, stimulating frequency, and stimulating pulse width can be remotely programmed. Since different spatial activation patterns and frequency parameters affect different spinal circuits, the array can be reconfigured, within limits, to bias its facilitating effects toward different functional activities, such as standing or voluntary movement or physiological responses such as blood pressure regulation. After determining the configurations for voluntary, standing, and blood pressure regulation, the individual will then begin his or her assigned group intervention for approximately 80 sessions for 6 hours each session. After intervention #1 is completed, the *post-intervention #1* assessments will be conducted (Appendix #1, post-intervention #1) and the individual will continue to complete his or her second assigned group intervention. *Post-intervention #2* assessments will be conducted after the completion of the second intervention. After about 40 sessions in each intervention, mid-training assessments will be conducted.

4. Experimental Groups/Interventions (n=36 research participants).

Two factors are varied in this study, the stimulation frequency (voluntary, cardiovascular, or standing) and the presence or absence of weight bearing stand training. Crossing these yields 4 possible interventions: A1, A2, B1, and B2, where A=no weight bearing stand training, B=with weight bearing stand training, 1=voluntary parameters Vol-scES and 2=cardiovascular parameters CV-scES. A description of each of the four different interventions is provided below.

Group A:

- Vol-scES during voluntary leg movement training while sitting or lying supine (A1).
- CV-scES during sitting or lying supine (A2).

Group B:

- Stand-ES during stand training + Vol-scES during voluntary leg movement training (B1).
- Stand-ES during stand training + CV-ES during sitting or lying supine (B2).

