3D. The LV Mass will be measured in 3D. Left ventricle inflow velocities during early and late diastole will be assessed using pulsed-wave and continuous wave Doppler at the mitral valve leaflet tips. Left ventricle outflow velocities will be assessed using pulsed-wave and continuous wave Doppler in the A4C or A3C views. Myocardial tissue velocities during systole, early diastole, and late diastole will be assessed using pulsed-wave tissue Doppler imaging of the septal wall at the level of the mitral annulus and at the right ventricular free wall. If we can get the full right ventricle in view we may measure the right ventricular area change and RV strain. From the A4C and A2C view the LA Volume will be measured along with the right upper pulmonary vein via pulse wave doppler. The RA Volume will be measured in the A4C view. LV strain may be assessed using parasternal short-axis at the papillary level, along with the A4C, A2C and A3C view using the program Echo Insight. Frame-by-frame twist and twist velocity values will be obtained by subtracting the apical rotation/rotation velocity from the basal rotation/rotation velocity. Myocardial dyssynchrony will also be examined by segmental analysis of LV mechanics. Standard dimensions, wall thickness, chamber volumes, systolic and diastolic function parameters will be calculated using commercially available software (e.g. Phillips and Echo Insight). Baseline comparisons to future measurements throughout training will be performed to assess for trends. Overall comparisons of measures from baseline to end of training will be performed using one-sided student's t-tests as the participants are their own controls with a $p < 0.05$ being considered statistically significant. For non-normally distributed variables the appropriate non-parametric test will be used for analysis (e.g. Kruskal-Wallis).

d. Arterial Pulse Wave Velocity (aPWV,m/s).

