For those participants not achieving independent standing during the stand training phase of the protocol, the home and community integration will include training in a customized standing device. Standing devices will be designed to match the level of assistance required to safely translate the training to the home environment. This phase can also include training of care givers or personal trainers to assist the participants in achieving safe and independent standing.

G. Statistical approaches.

For the primary aims (comparing to baseline), paired sample t-tests will be used the primary endpoints (hypotheses 1a, 1b, 1c) comparing the results at the end of the second intervention period to the baseline period.

For the secondary aims, each endpoint will be analyzed separately with a common linear model framework. We fit a linear model with effects for each stimulation setting (voluntary, cardiovascular, and standing) and an effect of weight bearing stand training within each stimulation setting. Thus, for example we have a coefficient which measures the additional benefit of weight bearing stand training and a stimulation setting over and above that stimulation setting alone. There are separate coefficients for the benefit of stand training within Vol-scES, CV-scES, and Stand-scES. Formally, we fit a linear model of the form

$$\begin{aligned} \text{Response} = & \beta_{\text{Vol-scES}} I_{\text{Vol-scES}} + \beta_{\text{CV-scES}} I_{\text{CV-scES}} + \beta_{\text{Stand-scES}} I_{\text{Stand-scES}} + \\ & \beta_{\text{VT}} I_{\text{Vol-scES and Training}} + \beta_{\text{CVT}} I_{\text{CV-scES and training}} + \\ & \beta_{\text{ST}} I_{\text{Stand-scES and training}} + \text{error} \end{aligned}$$

where the β terms give the regression coefficients and I_X is an indicator variable equal to 1 if X occurs and 0 otherwise. The indicator variables function to only include the coefficients of the model for treatments the participant actually receives. Thus, for a participant receiving CV-scES and stand training, the model would reduce to

$$\text{Response} = \beta_{\text{CV-scES}} + \beta_{\text{CVT}} + \text{error}$$

Due to the partial crossover, no carryover effects are included in the model (sensitivity analyses using only the first period data will also be summarized). Random effects for each subject may be included when appropriate.

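### The only rank test named for the within-participant echocardiography comparisons, Kruskal-Wallis, is an undirected test for independent groups; following it would ignore the pairing and can cost much power

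*Protocol*

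**What the plan says.** The Analysis paragraph of Protocol III.D.2.c (Echocardiography) describes two comparisons, both within participants.

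- Over time: "Baseline comparisons to future measurements throughout training will be performed to assess for trends".
- Start to finish: "Overall comparisons of measures from baseline to end of training will be performed using one-sided student's t-tests as the participants are their own controls", with p below 0.05 as the criterion.

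The fallback follows at once: "For non-normally distributed variables the appropriate non-parametric test will be used for analysis (e.g. Kruskal-Wallis"). No other non-parametric test is named there, and no comparison between arms is described.

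Appendix 1 schedules echocardiography in the same people at screening, before usual care, before and after implantation, periodically during the intervention, after each of the two interventions, and at follow-up.

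III.G (Statistical approaches) states that "paired sample t-tests will be used the primary endpoints (hypotheses 1a, 1b, 1c"), and uses linear models for the secondary aims. It names no rank-based alternative.

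**The concern.** A fallback should answer the same question as the test it replaces, with fewer distributional assumptions. Kruskal-Wallis changes the question in two ways.

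- **Pairing.** It treats baseline and later values as coming from different people. Stable differences between participants, which a paired test removes, stay in as noise. This applies to the two-visit comparison and to the comparison over several visits.
- **Direction.** The t-test for baseline to end of training is one-sided. Kruskal-Wallis with two groups amounts to a two-sided rank-sum test.

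Non-normal echocardiographic measures would therefore be tested more strictly than normal ones in the same table, for a reason unrelated to the treatment. With 9 participants per randomised group, little sensitivity can be spared.

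**Working it through.** The protocol states no power or error figure for echocardiography, so there is none to reproduce.

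**Inputs**

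- n = 9 (one randomised cohort), 18 (Group A or Group B) and 36 (all), from III.B.4 and Table 1. III.B also gives n=6 per study group; that figure is not used here.
- Level 0.05 and a one-sided paired comparison, from III.D.2.c.
- Assumed, because the protocol gives no values: a log-normal measure (log-scale SD 0.6), a shift of 0.5 SD on the log scale, and a correlation rho between visits of 0 to 0.7 on the log scale.

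**Step 1: type I error in closed form.** With two visits of n values each and N = 2n, the statistic is

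H = 12/(N(N+1)) × (R1²/n + R2²/n) − 3(N+1).

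This equals z², where z is the standardised rank sum for independent groups. If the visits have rank correlation rs, the variance of z under the null is about 1 − rs instead of 1. The actual error is then about 2 × [1 − Φ(1.96/√(1 − rs))]. For normal data on the log scale, rs = (6/π) × arcsin(rho/2).

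| rho | rs | 1.96/√(1 − rs) | approximate error | simulated error |
|---|---|---|---|---|
| 0 | 0 | 1.96 | 5.0% | about 5% |
| 0.3 | 0.288 | 2.32 | 2.0% | 2.3–2.4% |
| 0.5 | 0.483 | 2.72 | 0.6% | 0.8–1.0% |
| 0.7 | 0.683 | 3.48 | 0.05% | 0.1–0.3% |

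The simulated column comes from the runs described in step 2, with the shift set to zero. The two-sided signed-rank test in those runs rejected 3.8–5.2% of the time.

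**Step 2: power by simulation.** 10,000 data sets per cell; Kruskal-Wallis by chi-square on 1 df, signed-rank exact.

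| n | rho | Kruskal-Wallis | signed-rank, two-sided | signed-rank, one-sided |
|---|---|---|---|---|
| 9 | 0.3 | 13.4% | 16.0% | 29.4% |
| 9 | 0.5 | 10.8% | 21.0% | 35.8% |
| 9 | 0.7 | 8.0% | 32.5% | 50.6% |
| 18 | 0.3 | 27.5% | 36.1% | 49.2% |
| 18 | 0.5 | 24.9% | 46.3% | 60.2% |
| 18 | 0.7 | 20.5% | 67.1% | 78.9% |
| 36 | 0.3 | 53.3% | 64.0% | 75.2% |
| 36 | 0.5 | 54.7% | 77.7% | 86.2% |
| 36 | 0.7 | 55.8% | 93.6% | 96.7% |

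An independent repeat with a different random seed agreed within simulation error.

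Relative loss against the two-sided paired test:

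- n=9: from 1 − 13.4/16.0 = 16% to 1 − 8.0/32.5 = 75%.
- n=36: from 1 − 53.3/64.0 = 17% to 1 − 55.8/93.6 = 40%.

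**Step 3: separating direction from pairing.** The step from one-sided to two-sided signed-rank is the cost of losing direction (at n=9 partly the coarseness of the exact test). The step from two-sided signed-rank to Kruskal-Wallis is the cost of losing the pairing. At rho 0.5:

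- n=9: 35.8 − 21.0 = 14.8 points for direction; 21.0 − 10.8 = 10.2 points for pairing.
- n=36: 86.2 − 77.7 = 8.5 points for direction; 77.7 − 54.7 = 23.0 points for pairing.

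**Step 4: where the loss is small or absent.** At rho 0 and n=9, Kruskal-Wallis has 16.3% power against 12.5% two-sided. With a 0.8 SD shift, n=36 and rho 0.5, it has 96.3% against 99.3%.

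**Step 5: a different calibration.** Here the shift is set so that the one-sided paired t-test has 80% power under normality. The one-sided signed-rank test and Kruskal-Wallis then compare as follows.

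- Normal data, n=9: 78% vs 42% at rho 0.5; 77% vs 20% at rho 0.7.
- Normal data, n=36: 78% vs 37% at rho 0.5; 78% vs 14% at rho 0.7.
- Skewed data, n=36: 89% vs 60% at rho 0.5; 88% vs 35% at rho 0.7.
- rho 0: about 78% vs 68–70% with normal data, and no loss with skewed data.

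**The case against.** The operative instruction is to use the appropriate test, and Kruskal-Wallis appears only as an example. The sentence before it says that participants are their own controls, so a careful analyst would choose a paired rank test, and the SAP, not seen here, may name one. III.G sends the primary hypotheses to paired t-tests and the secondary contrasts on cardiac measures to linear models, so the fallback governs only the pre/post reporting of echocardiographic variables. The error is conservative, and its size rests on assumed correlations and shifts.

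Most of this stands, and it limits the weight of the point. It does not make the example right. The protocol names one rank test for a paired comparison, and that test is for unpaired data. This is an error in what is written, not a detail left to the SAP.

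Two narrower replies also have some force. First, one-sidedness is stated only for baseline to end of training, so the complaint about direction applies there and not to the comparison over several visits; the Friedman test is itself undirected. Second, the own-controls wording already implies paired t-tests, so saying so outright is only a clarification.

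**Conclusion.** The concern holds. Kruskal-Wallis is the wrong example for these comparisons: it ignores the pairing throughout and drops the direction of the baseline-to-end comparison. Under the assumptions above, using it would cost 16% to 75% of the power of a two-sided signed-rank test at n=9, and 17% to 40% at n=36, for correlations of 0.3 to 0.7. The loss is larger against the one-sided test, and it vanishes against the two-sided test as the correlation approaches zero.

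The consequence depends on an analyst following the example. It can hide real change but creates no false-positive claims. It is confined to echocardiographic measures judged non-normal and does not reach the tests in III.G. It should be corrected, but it does not threaten the trial's main conclusions.

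**What to change.** In III.D.2.c, state that the t-tests are paired. Replace the Kruskal-Wallis example with the Wilcoxon signed-rank test on within-participant differences for two visits, and the Friedman test for more than two. Give the signed-rank test the same sidedness as the t-test it replaces.

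The cost is one sentence; no data, visits or participants are added. One caution: the signed-rank test assumes roughly symmetric differences, so strongly skewed measures may need a log transform first, and the text should allow for that.

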Procedure: This assessment will be measured non-invasively and calculated by dividing the distance between measurement (meters) sites by the pulse transit time (seconds). The subject will be in the supine position during the assessment. The distance between the arterial measurement points will be assessed using measuring tape along the surface of the body, held parallel to the testing table. The pulse transit time will be determined from the arterial blood pressure waves, which are collected at each artery, recorded from special sensors. A Complior Pulse Wave and Central Pulse Analyzer (Aim Medical, Vincennes, France) sensors will be applied to the carotid, femoral, brachial, or other arterial sites. A minimum of 10 consecutive pulses are required for analysis. This procedure has been previously described by Phillips et al 2014. Heart rate will be recorded using a single lead electrocardiogram (ECG) (ModalML 123, AD Instruments Inc, Colorado Springs, CO). This may be done with CV-scES.

Analysis: The Complior software package provides experimental acquisition and data report functions. Upon completion of the test, the software generates a document containing the Pulse Wave Velocity outcome measures and percentile for each participant.

e. Sympathetic Skin Responses (SSR).

Procedure: Sympathetic skin responses (SSR): The SSR will be elicited by stimulation of supra-orbital, median and/or tibial nerves, and recorded bilaterally and simultaneously from both hands and feet to assess the extent of disruption to spinal autonomic pathways. Five to ten electrical stimuli (duration 0.2 ms; intensity 3-60mA) will be applied Supra orbital nerve, the median nerve and posterior tibial nerve, in random order and with variable and long-time delays to minimize habituation. This may be done with CV-scES.

Analysis: The SSR recordings are among the frequently utilized techniques for the evaluation of integrity and functional capacity of the autonomic circuits after SCI [101, 102, 114, 117]. The outcomes will be calculated as a number of recognizable responses out of 10 stimulations, and averaged latency and averaged amplitude [118].

f. Vascular Ultrasound.

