Appendix #1

Appendix 1. Frequency of Outcomes for Aims 1 – 3.

Assessment Category #=with and without stim	Assessments	Pre-screen	Screen	Pre-Usual Care	Pre-implant	Post-Implant/ Pre-Intervention	Weekly	Periodic Through Intervention	Monthly	Post-Intervention #1	Post-Intervention #2	Follow Up(s)
Medical	SC MRI	X	or X									
	ASIA		X	X	X					X	X	
	Physician and PT Medical		X	X	X					X	X	X
	Pregnancy	X	X									
	Blood Work		X	X	X					X	X	X
	Drug Testing	X	X	X	X	X	X	X		X	X	X
Voluntary	MMR		X									
	FNPA		X	X	X	X#				X#	X#	X#
	NRS trunk and leg score		X	X		X#		X#		X#	X#	X#
	Lower Extremity Torque with EMG					X#		X#		X#	X#	X#
	Neuromuscular Voluntary Movement Assessments					X#		X#		X#	X#	X#
Cardiovascular	Ambulatory BP monitoring		X	X				X	X	X	X	X
	Ambulatory HR monitoring		X	X				X	X	X	X	X
	12 lead ECG				X					X	X	
	Orthostatic Stress Test		X	X	X	X#		X#		X#	X#	X#
	Vascular Ultrasound			X	X	X#		X#		X#	X#	X#
	Echo-cardiography		X	X	X	X#		X#		X#	X#	X#
	Arterial pulse wave velocity		X	X	X	X#		X#		X#	X#	X#
	Sympathetic skin responses				X					X	X	
Stand	Dexa		X		X					X	X	X
	Independence levels during stand -			X	X	X#	X#	X#		X#	X#	X#
	Standing Assessments				X	X#		X#		X#	X#	X#
Respiratory	Pulmonary Function Test		X		X	X#				X#	X#	X#
	Respiratory Motor Control Assessment		X		X	X#				X#	X#	X#
	Resting metabolic rate		X	X	X					X	X	X

Assessment Category #=with and without stim	Assessments	Pre-screen	Screen	Pre-Usual Care	Pre-implant	Post-Implant/ Pre-Intervention	Weekly	Periodic Throughout Intervention	Monthly	Post-Intervention #1	Post-Intervention #2	Follow Up(s)
Bladder	Urodynamics		X	X	X					X	X	X
	Bladder Questionnaire			X	X					X	X	X
	Urinalysis			X	X					X	X	X
	Ultrasound			X	X					X	X	X
Bowel	Bowel Questionnaire			X	X					X	X	X
	Anorectal Manometry			X	X					X	X	X
Sexual Function	International Dataset (Males)			X	X					X	X	X
	International Dataset (Females)			X	X					X	X	X
Quality of Life	SCI-QOL		X		X					X	X	X
	SCI-FI		X		X					X	X	X
	PROMIS		X		X					X	X	X
	EQ-5D-3L		X		X					X	X	X

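### The sympathetic skin response count uses a fixed denominator of 10 although five to ten stimuli are permitted, so it could move with the number of stimuli delivered

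*Protocol*

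**What the plan says.** Both statements stand in the current text of Protocol section III.D.2.e, Sympathetic Skin Responses (SSR).

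- Acquisition (Procedure paragraph): "Five to ten electrical stimuli (duration 0.2 ms; intensity 3-60mA) will be applied". On the nerves it says: "The SSR will be elicited by stimulation of supra-orbital, median and/or tibial nerves". Recording is bilateral, from hands and feet. The paragraph does not say whether the range of five to ten applies to each nerve or to the whole test.
- Scoring (Analysis paragraph): "The outcomes will be calculated as a number of recognizable responses out of 10 stimulations". Averaged latency and averaged amplitude are listed as further SSR outcomes.

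Appendix 1 lists "Sympathetic skin responses" under Cardiovascular with three marks. In the flattened table these appear to be pre-implant, post-intervention #1 and post-intervention #2.

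The section does not say when five rather than ten stimuli are given. It does not hold the number constant within a participant, and it does not adjust the count when fewer than ten are given.

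**The concern.** A count of responses can be compared between tests only if the number of trials is the same or the count is divided by it. Here the number of trials may vary and the denominator may not. Read literally, the rule understates the response rate whenever fewer than ten stimuli are delivered.

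The test is repeated over time and is meant to show how far spinal autonomic pathways are disrupted. If the number of stimuli changed between visits, that change could be read as loss or recovery of pathway function.

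Elsewhere the protocol avoids this. Vascular ultrasound (III.D.2.f) also allows a variable number of replicates, three to seven cardiac cycles, but reports their mean, which does not grow with the number of cycles.

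**Working it through.** **Inputs**

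- Stimuli delivered, n: 5 to 10 (III.D.2.e, Procedure).
- Denominator: 10, fixed (III.D.2.e, Analysis).
- Response probability per stimulus, p: not in the documents. Assumed to be the same for every stimulus, and taken at 20%, 60% and 100% to show the range.
- Cohort size: 9 per initial intervention (Table 1 in section III.B).

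This section has no sample size, power or alpha figure to reproduce. The only stated figure is the denominator of 10, which agrees with the procedure only at the top of its permitted range.

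**Expected count out of 10**, for one scored series of n stimuli: n × p.

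| p (assumed) | n = 5 | n = 7 | n = 10 | Difference, 10 vs 5 |
|---|---|---|---|---|
| 20% | 5 × 0.2 = 1 | 7 × 0.2 = 1.4 | 10 × 0.2 = 2 | 1 |
| 60% | 5 × 0.6 = 3 | 7 × 0.6 = 4.2 | 10 × 0.6 = 6 | 3 |
| 100% | 5 × 1 = 5 | 7 × 1 = 7 | 10 × 1 = 10 | 5 |

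The ratio is 10/5 = 2 at every p, so the same response rate can give a two-fold difference in the count. The largest absolute difference is 5 points on the 0-10 count, or 50 percentage points if the count is read as a proportion of 10.

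**Effect on a cohort mean.** If one of 9 participants shifts by the maximum of 5 points for this reason alone, the cohort mean moves by 5/9 = 0.56 points.

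**Does the unit of counting matter?** There are two readings of the range:

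- Total over the nerves: 10 is the maximum and fits only a full series.
- Per nerve: a denominator of 10 for each nerve again fits only when all ten are given. Pooled over nerves, the total would be 10 to 20 for two nerves and 15 to 30 for three, and 10 is then not the denominator in general.

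The mismatch survives both readings. The table applies to a series scored by itself, for example one nerve at one recording site.

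**After the repair.** Responses divided by stimuli delivered has expectation (n × p)/n = p. At p = 60% this is 3/5 = 4.2/7 = 6/10 = 0.60.

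**The case against.** The strongest reply is that the analysis sentence is loose wording and not a scoring rule. It may describe a full series of ten, or a rate, and the handling of shorter series may be set out in a statistical analysis plan that is not at hand. This is possible. But the protocol itself states both the range and the denominator, and they disagree. An analysis plan could rescale the count only if the number delivered is recorded, and this section does not ask for that.

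The second reply concerns reach, and most of it stands. A reader might infer that before/after comparisons of this measure are biased. The documents do not support that. Bias needs the number of stimuli to differ between visits or between groups, which the protocol permits but neither prescribes nor predicts. If a participant receives the same number at every visit, the count still compares like with like within that participant.

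A reader might also infer that anyone given five stimuli is capped at a score of 5. That holds only if five is the total, or if each nerve and site is scored separately. The text settles neither.

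Third, importance is limited. No hypothesis in section III.C names SSR, and section III.D.2.e specifies no test for it. The before/after use is inferred from Appendix 1 and the general approach in section G. Averages of latency and amplitude do not scale with the number of stimuli; only their precision depends on it.

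**Conclusion.** The point holds as a minor inconsistency in one stated rule. The fixed denominator of 10 is right only when ten stimuli are delivered. With fewer, the count understates the response rate, by up to half at five stimuli.

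The possible artefact between a five-stimulus and a ten-stimulus series is 1 point at a 20% response rate, 3 at 60% and 5 at 100%. These rates are assumptions. The 100% case is a ceiling that may be far from what is seen after severe spinal cord injury. The figures also assume a constant response rate over the series, and a score taken per series.

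The documents do not show that stimulus numbers will differ, so they do not support saying that the SSR results will be distorted. They support saying that the count could be distorted and that nothing in the section prevents it. The latency and amplitude outcomes are not affected in this way, and no named primary endpoint is involved.

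**What to change.** Reconcile the Procedure and Analysis sentences in section III.D.2.e in one of two ways:

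- Record the number of stimuli delivered in each series, and define the outcome as recognizable responses divided by stimuli delivered, per stimulated nerve and recording site.
- Use one constant number of stimuli for all participants and visits, with the denominator equal to that number.

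Either way, the text should say whether the number applies per nerve or to the whole test. The second option also avoids relying on a constant response rate through a series. This is relevant because the procedure itself takes steps against habituation. The documents do not show which number is intended, so that is for the investigators to state.

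The cost is about one line of protocol text and, for the first option, one number recorded per series. No extra assessment is needed. For tests already done, the proportion can be computed wherever the number delivered was logged.
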